#### 4.1 TREATMENT ASSIGNMENT PROCEDURES

Phase one: Participants will receive stimulation to either the frontal or parietal cortex in a randomized and counter-balanced sequence for the fourth and fifth session. Randomization and counterbalancing is performed by a script that generates a spreadsheet to stimulation ID mapping. Participants are randomized upon entering the fourth session of the experiment. Thus, there is no influence of the experiment on which sequence the participant will receive. Stimulation types are randomized and counter-balanced by a script at the time of the session and defined as theta, alpha, arrhythmic-theta, and arrhythmic-alpha. It should be noted that all analyses are controlled by a within-session contrast that accounts for general sequence effects.

Phase two: Participants are randomized to receive stimulation to both the frontal and parietal cortex in either theta or alpha frequency for both of the fourth and fifth session. A similar randomization procedure will be used as in phase one. Stimulation types are randomized and counter-balanced within a session by a script: in-synchrony, anti-synchrony, arrhythmic-synchrony, and arrhythmic-independent. It should be noted that all analyses are controlled by a within-session contrast by comparing to arrhythmic stimulation.

The primary analysis of the experiment is controlled within-session as a contrast with the arrhythmic control conditions. The difference in site of stimulation for phase one and the auditory difference between theta and alpha stimulation (theta is audibly slower than alpha) precludes double-blinding as the researcher will be aware of this difference in running the experiment. In other words, the study cannot be blinded and there is no attempt to blind the study. Furthermore, the control for each stimulation condition is self-contained within each session. The stimulation sessions for each phase consists of four stimulation conditions (described above) and two task conditions (retro-cue to the left visual field and retro-cue to the right visual field), thus there are a total of 8 conditions total for phase 1 and 4 conditions total for phase 2. With 600 trials per session, then will be 75 trials of each condition for phase 1 and 150 trials of each conditions for phase 2. The order of these trials is randomized for each session for each participant via a script.

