forms of arrhythmic stimulation are used: arrhythmic-in-synchrony stimulation delivers simultaneous stimulation to the two sites, but there is no consistent frequency component to the stimulation. Thus, activity in the two sites may be synchronized but not in a frequency-specific manner. The second control condition for stimulation is arrhythmic-independent where two trains of TMS are delivered in random patterns. There is no synchronization between the two pulse trains. Arrhythmic-independent controls for frequency and synchrony specificity of stimulation. All analyses will be performed on the difference from condition-matched arrhythmic TMS (in-phase minus arrhythmic-in-synchrony and anti-phase minus arrhythmic-independent). The key analyses are built upon a three-way design: with factors TMS frequency (theta and alpha), TMS alignment (in-phase and anti-phase), and cue direction (left and right retro-cue).

**Aim 6 (primary outcome):** Stimulation that is delivered in-phase to frontal and parietal cortex in the theta frequency is hypothesized to increased working memory capacity relative to anti-phase theta stimulation. Working memory capacity is quantified using Pashler's metric (see Aim 1). We will perform a two-way repeated-measures ANOVA with a between participants factor of TMS frequency (theta and alpha) and within-participants factor of TMS alignment (in-phase and anti-phase). We hypothesize to find a significant interaction ( $p < 0.05$ ) between TMS frequency and TMS alignment such that in-phase TMS in theta-frequency increases working memory capacity. Post-hoc t-tests will be performed using Tukey's method to control for multiple comparisons. *Sensitivity analysis:* Similar to aim 1, the impact of stimulation on hit rate, false alarm rate, and overall accuracy will be calculated. The robustness of these effects will be estimated using an individual differences analyses where baseline performance is used as a covariate to improve model estimation. Finally, the titration of working memory load by participant will be added as a covariate to explore if this factor changes the model estimation. These are framed as exploratory analyses.

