**Aim 7 (primary outcome):** Stimulation that is delivered in-phase to frontal and parietal cortex in theta frequency is hypothesized to increase functional connectivity between the regions in a frequency specific manner. Functional connectivity will be measured using weighted phase lag index (WPLI). To calculate WPLI, first Morlet wavelet convolution is performed to extract instantaneous phase and amplitude for the frequency of interest for the two target sites. Next, the cross-spectral density is calculated (one signal multiplied by the complex conjugate of the other). From the cross-spectral density the imaginary component of the resulting signal is extracted. Then those imaginary values are averaged over the time frame of instance (here, the second half of the stimulation train). Finally, the magnitude of the resulting vector is taken to be the WPLI. This metric quantifies the consistency of phase lag between the two target regions and is weighted towards signals with a 90 or 270 degree offset to address a common confound in EEG, volume conduction. We hypothesize that in-phase theta-frequency stimulation will increase theta-frequency WPLI strength between frontal and parietal cortex. In addition, we hypothesize that in-phase theta frequency stimulation will increase WPLI magnitude for retro-cues to the right visual field greater than the increase for stimulation with a retro-cue to the left visual field. This hypothesis is motivated by the finding that the left hemisphere processes information for the contralateral visual hemifield and that theta oscillations are linked to the active processing of information. Using a two-way ANOVA with factors for TMS frequency (theta or alpha) and retro-cue direction (left or right), we hypothesize a significant interaction ( $p < 0.05$ ) between TMS frequency and retro-cue direction such that WPLI magnitude is the greatest for theta-frequency stimulation with a retro-cue to the right visual field. Post-hoc t-tests will be performed using Tukey's method to control for multiple comparisons. *Sensitivity analysis:* The frequency, topographic, and spatial specificity of these effects will be explored. Similar to Aim 2, the time-course of WPLI can be estimated using a sliding window to demonstrate if functional connectivity rises and peaks at the end of the stimulation train. Furthermore, the topographic increase in functional connectivity will be quantified across the scalp to see if the effect is specific to the targeted regions. Finally, the frequency specificity will be explored by calculating functional connectivity across the full spectral range (2-30 Hz) and the specificity of connectivity changes in frequency domain will be displayed. Together, these analyses will establish the robustness

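### Aim 7's only pre-specified p < 0.05 test is the frequency-by-cue-direction interaction, which addresses the added lateralised hypothesis and not the first one, that in-phase theta stimulation raises fronto-parietal theta WPLI

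*Combined protocol and SAP*

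**What the plan says.** Section 2.3 lists Aim 7 as a primary outcome and section 11.1 gives its analysis. The first hypothesis carries no condition on cue direction: "We hypothesize that in-phase theta-frequency stimulation will increase theta-frequency WPLI strength between frontal and parietal cortex". A second is then attached: "In addition, we hypothesize that in-phase theta frequency stimulation will increase WPLI magnitude for retro-cues to the right visual field greater than the increase" for left cues.

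The test named is a two-way ANOVA: "Using a two-way ANOVA with factors for TMS frequency (theta or alpha) and retro-cue direction (left or right), we hypothesize a significant interaction". The 0.05 threshold belongs to that interaction alone: "we hypothesize a significant interaction ( $p < 0.05$ ) between TMS frequency and retro-cue direction". Follow-up is generic: "Post-hoc t-tests will be performed using Tukey's method to control for multiple comparisons". No contrasts are listed, and the text does not say whether these tests depend on a significant interaction.

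Three other statements matter:

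- The analysed quantity is control-subtracted: "All analyses will be performed on the difference from condition-matched arrhythmic TMS (in-phase minus arrhythmic-in-synchrony and anti-phase minus arrhythmic-independent". An increase therefore means a mean difference above zero.
- Frequency is a between-participant factor in phase two (section 4.1): "Participants are randomized to receive stimulation to both the frontal and parietal cortex in either theta or alpha frequency".
- The opening paragraph of section 11.1 has any test with p above 0.05 reported as inconclusive.

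**The concern.** The hypothesis that opens Aim 7 concerns the level of WPLI under in-phase theta stimulation. The named test concerns a difference between cue sides, compared between frequency arms. These are separate questions, and the first has no test and no decision rule.

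Two errors could follow on a primary outcome. A real rise in theta connectivity that does not depend on cue side would be reported as inconclusive. A difference between cue sides with no net rise would meet the stated criterion and could be read as confirming increased connectivity. The sensitivity analyses do not fill the gap: they describe time course, topography and spectrum, and section 11.1 says that they rely on the analysis already established.

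**Working it through.** **The plan's own figure.** Section 11.2 gives 48 participants for 95% power at an effect size of 0.532. A two-sided paired t-test at 0.05 reproduces it: non-centrality 0.532 × √48 = 3.686 on 47 df, power 95.05%. That effect is the phase-one site-by-frequency interaction on working memory capacity. Section 11.2 gives no figure for WPLI.

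**The contrast.** Let θR, θL, αR and αL be the mean control-subtracted WPLI by frequency arm and cue side. The named interaction is (θR − θL) − (αR − αL). For a theta rise of δ with both cues and no alpha effect, it is (δ − δ) − (0 − 0) = 0. The rejection rate is then 5% for any δ and any N. This is algebra and needs no assumption about variances.

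**Assumptions for the comparison.** Section 3 gives 48 completers per phase. The documents give no allocation ratio, WPLI standard deviation, cue correlation or WPLI effect size. I assume 24 per arm, SD 1 per cue and correlation ρ = 0.5, with a range of 0.2 to 0.8. Tests are two-sided at 0.05, using the non-central t distribution.

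- SD of a participant's right-minus-left difference: √(2(1 − ρ)) = 1.000
- SD of a participant's average over cues: √((1 + ρ)/2) = 0.866
- Interaction non-centrality: [(θR − θL) − (αR − αL)] / 1.000 × √(24/2), 46 df
- Theta-arm test against zero: mean / 0.866 × √24, 23 df
- Frequency main effect: difference in means / 0.866 × √(24/2), 46 df

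*Equal 0.5 SD rise for both cues.* Non-centralities are 0 for the interaction, 0.5/0.866 × 4.899 = 2.828 for the theta arm and 0.5/0.866 × 3.464 = 2.000 for the main effect.

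*Theta effects of −0.5 (left) and +0.5 (right), average zero.* The interaction has non-centrality 1.0 × 3.464 = 3.464; the other two have 0.

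*Rise of 0.8 SD with right cues only.* The interaction has 0.8 × 3.464 = 2.771. The cue average is 0.4, giving 0.4/0.866 × 4.899 = 2.263 for the theta arm and 0.4/0.866 × 3.464 = 1.600 for the main effect.

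| Theta effect | Interaction | Theta arm against zero | Frequency main effect |
|---|---|---|---|
| Equal, 0.5 SD | 5% | 77% (70–86%) | 50% (43–59%) |
| −0.5 / +0.5 SD | 92% (76% to over 99%) | 5% | 5% |
| Right cue only, 0.8 SD | 77% (57–99%) | 58% (51–68%) | 35% (30–42%) |

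Brackets give the range over ρ = 0.2 to 0.8.

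**Tukey follow-up.** In a simulation (20,000 runs per scenario, same assumptions, ρ = 0.3 to 0.7, equal rise of 0.532 SD), same-cue theta-versus-alpha comparisons found the rise in 31–36% of runs if always performed. If performed only after a significant interaction, they found it in 3–4%. Either way they compare cells with each other and not with arrhythmic control.

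**The case against.** The plan predicts a larger rise with right cues, and if the rise is strongly lateralised the interaction is the better test: 77% against 35% for the frequency main effect in the right-cue-only case above. This stands. A reader might infer that the named test can never detect a theta effect. It cannot detect one that is equal across cues, and the first hypothesis is not limited to a lateralised rise.

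The plan also requires estimates with confidence intervals, and every value is a difference from arrhythmic TMS. The theta-arm means would therefore be visible, and a pure cue-side difference could be recognised. That is a safeguard in reporting, but it sets no rule for deciding a primary hypothesis.

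A reader might take the frequency main effect, which the ANOVA produces anyway, as the natural test of the first hypothesis. Section 11.1 attaches no hypothesis to it under Aim 7, although Aim 8 does name a main effect. It also compares theta with alpha, so it could be significant because alpha stimulation lowered WPLI while theta did nothing. It speaks to frequency specificity, which Aim 7 also claims, and not to an increase over control.

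Finally, phase two is described as a design "with factors TMS frequency (theta and alpha), TMS alignment (in-phase and anti-phase), and cue direction (left and right retro-cue", and Aim 7's ANOVA leaves alignment out. A reader might infer that a required factor was dropped. The documents do not support that: Aim 7 makes no in-phase versus anti-phase claim, Aims 6 and 8 test alignment, and Aims 1, 2 and 5 also use two-way slices of a three-way design.

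**Conclusion.** The point holds and should be settled before the Aim 7 analysis. As written, the plan would decide the first hypothesis of a primary outcome with a contrast that is blind to a rise common to both cues. The 5% rejection rate in that case follows from the contrast itself. The comparison figures of 77% and 50% rest on the assumed 24 v 24 split, unit SD and cue correlation, and are illustrative.

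The point is limited to the a priori test that carries a threshold. The Tukey tests are also named, but without contrasts or a gating rule and without a comparison with control. The study's pilot label and the wording that large p-values are inconclusive soften the consequence but do not supply the missing test.

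**What to change.** Rewrite the Aim 7 analysis as a fixed sequence, each step at 0.05:

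1. Primary test: the theta-arm mean of in-phase minus arrhythmic-in-synchrony theta WPLI, averaged over cue direction, against zero, with its confidence interval.
2. The theta-versus-alpha main effect on theta WPLI, for frequency specificity.
3. The frequency-by-cue-direction interaction, for the lateralised hypothesis.

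State the role of the Tukey comparisons and whether they depend on an earlier step. Adding alignment as a factor is optional and not part of this fix.

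The change is SAP wording; data and model family stay the same. The cost falls on the lateralised hypothesis, which moves to the last step. In the right-cue-only 0.8 SD example, it could be claimed in at most about 35% of trials, the power of step 2, against 77% when tested alone. The team should accept that order knowingly.

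The change log in section 1.5 dates version 7.0 to September 2025 and the entry reflecting IRB submission to January 2021. Data may therefore already be in hand, though the documents do not say so. If any phase-two WPLI results have been seen, the change should be dated, justified and reported as made after that point.

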Aim 2 (primary outcome): Stimulation is hypothesized to increase the targeted frequency of stimulation relative to arrhythmic stimulation. This aim will provide evidence of target engagement, i.e. that stimulation is effective at modulating the targeted rhythm. Using Morlet wavelet convolution, the amplitude of theta and alpha oscillations will be estimated during task performance. The average across trials for each conditions will be calculated and baseline corrected using decibels to the time before the encoding array (700 to 300 milliseconds). Then, the average amplitude within the individual theta (ITF  $+$ /- 1 Hz) and alpha frequency (IAF  $+$ /- 1 Hz) band will be calculated for the second half of the train of TMS pulses. Previous research has shown that amplitude increase from stimulation increases over the course of the TMS train. Frontal-theta and parietal-alpha amplitude values will be submitted to a two-way repeated-measures ANOVA with TMS frequency by TMS site. We hypothesize to find a significant interaction ( $p < 0.05$ ) between TMS site and TMS frequency such that theta amplitude in frontal cortex increases greater for TMS to frontal in theta frequency and alpha amplitude in parietal cortex increases greater for TMS to parietal cortex in alpha frequency. Post-hoc t-tests will be performed using Tukey's method to control for multiple comparisons. *Sensitivity analysis*: To understand the specificity of this effect, the time-course for the impact of stimulation of amplitude will be plotted as well as the topographic plot for our effects. Cluster analysis will be used to estimate the spread of our effect in time and space. These analyses provide evidence to the robustness of the

impact of stimulation on amplitude.

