
of our a priori effect. Furthermore, these confirmatory sensitivity analyses avoid the multiple comparisons problem by relying on the initially established analyses.

**Aim 8 (secondary outcome):** Stimulation that is delivered in-phase is hypothesized to decrease the relative phase difference (phase lag) between the frontal and parietal cortex, whereas anti-phase stimulation is hypothesized to increase the phase lag. If stimulation entrained neural activity directly to the stimulation train, then this pattern of phase lag differences would be expected (because in-phase stimulation is delivered with zero phase lag and anti-phase stimulation is delivered with a phase lag). To calculate phase lag, first Morlet wavelet convolution is performed to extract instantaneous phase and amplitude for the frequency of interest for the two target sites. Next, the cross-spectral density is calculated (one signal multiplied by the complex conjugate of the other). From the cross-spectral density the phase angle is extracted, this is the phase lag. Then those phase lag values are averaged over the time frame of instance (here, the second half of the stimulation train). Finally, the angle of the resulting vector is taken to be the average phase lag. This metric quantifies the degrees of phase lag between the two target regions. Using a two-way ANOVA with factors for TMS frequency (theta or alpha) and TMS alignment (in-phase or anti-phase), we hypothesize a significant main effect ( $p < 0.05$ ) of TMS alignment such that phase lag is different between in-phase and anti-phase where in-phase decreases the phase lag and anti-phase increases the phase lag. We also hypothesize that this effect will be strongest for theta-frequency stimulation, which is hypothesized to be revealed as a significant main effect between TMS frequency and TMS alignment. Post-hoc t-tests will be performed using Tukey's method to control for multiple comparisons. *Sensitivity analysis:* Similar to Aim 7, the spread of stimulation effects in time, space, and frequency will be explored.

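### Aim 7 calls its searches over time, scalp and 2-30 Hz confirmatory and free of multiplicity, but the pre-specified interaction test protects only itself

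*Combined protocol and SAP*

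**What the plan says.** Section 11.1 gives Aim 7 one primary test: the interaction of TMS frequency (theta or alpha) with retro-cue direction on WPLI, at p < 0.05. Tukey's method is named for the post-hoc t-tests of that ANOVA.

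The sensitivity analysis opens with "The frequency, topographic, and spatial specificity of these effects will be explored" and lists three searches:

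- Time: "the time-course of WPLI can be estimated using a sliding window to demonstrate if functional connectivity rises and peaks at the end" of the train.
- Scalp: "the topographic increase in functional connectivity will be quantified across the scalp to see if the effect is specific to the targeted regions".
- Frequency: "calculating functional connectivity across the full spectral range (2-30 Hz) and the specificity of connectivity changes in frequency domain will be displayed".

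The plan says that together these will show the pre-specified effect to be robust, and closes with "these confirmatory sensitivity analyses avoid the multiple comparisons problem by relying on the initially established analyses".

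Elsewhere in 11.1 the treatment differs. Aim 2 adds "Cluster analysis will be used to estimate the spread of our effect in time and space", and Aims 3 and 5 repeat cluster analysis. Aims 1 and 6 say of their sensitivity analyses: "These are framed as exploratory analyses". Aim 8 says that the spread of its effects in time, space and frequency will be explored in a similar way to Aim 7.

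**The concern.** The closing sentence credits the searches with a protection they do not have. Fixing one test in advance limits the error of that test. It does not limit the chance that something turns up when other times, sites and frequencies are examined.

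Conclusions depend on these searches. The scalp map is the only place where regional specificity is examined, because the primary ANOVA includes no other sites. The 2-30 Hz scan is the only look at the rest of the EEG spectrum. Chance findings outside the target band or sites would count against specificity. Chance findings in neighbouring windows could be taken as support for the expected time course. With the searches labelled confirmatory, either could be reported uncorrected as a result of the trial.

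**Working it through.** **The plan's own figures.** The plan gives no error rate or number of looks for the Aim 7 searches, so there is no figure to reproduce on this point. Its sample sizes do reproduce: a two-sided paired t-test at 0.05 with 95% power needs 48, 21 and 44 participants for effect sizes 0.532, 0.83 and 0.56, as section 11.2 states. They do not bear on multiplicity.

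**Inputs.**

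- From the plan: the 2-30 Hz range, the 0.05 level used throughout 11.1, 48 participants, and theta or alpha assigned between participants in phase two (section 4.1).
- Assumed: 1 Hz steps, a target band of ±1 Hz (stated for Aim 2, not for Aim 7), a 24/24 split, and a test of each bin at 0.05. The plan gives no step size and no per-bin rule.

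**Independent bins.** From 2 to 30 Hz in 1 Hz steps there are 29 bins. Removing 3 target bins leaves 26.

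- Expected false positives: 26 × 0.05 = 1.3.
- Chance of at least one: 1 − 0.95^26 = 0.736, or 74%.

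**Correlated bins.** Neighbouring wavelet estimates overlap, so independence gives the upper end. A simulation used 10,000 runs, 24 versus 24 participants, 29 bins with first-order autoregressive correlation, and a true standardised effect of 1.0 in three theta bins. It counted runs with at least one false positive among the 26 null bins, given that the test at the centre of the theta band was significant (92% to 93% of runs):

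| Neighbour correlation | Chance of at least one false positive |
|---|---|
| 0 | 74% |
| 0.5 | 68% |
| 0.8 | 51% |
| 0.9 | 37% |
| 0.95 | 24% |

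**Reliance on the primary test read as a gate.** Suppose the searches were read only after a significant primary test. If no bin had a true effect, the chance that the primary bin and some non-target bin were both significant would be 3.6% to 4.5%, so a gate would hold in that case. If the theta effect is real, which is when specificity would be claimed, the gate opens in most runs and the 24% to 74% in the table applies. No gate is written in any case.

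**What correction does.** Bonferroni over 29 bins uses 0.05 / 29 = 0.00172 per bin, and for independent bins the family-wise error is 1 − (1 − 0.00172)^29 = 4.9%. A maximum-statistic threshold for the same 29 bins is |t| = 3.31 at correlation 0, 3.10 at 0.9 and 2.89 at 0.95, each holding the error over the scan at about 5%.

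**The case against.** The strongest reply is that the maps are descriptive. The plan speaks of exploring, estimating, quantifying and displaying, and attaches p < 0.05 in Aim 7 only to the interaction. The closing sentence could then mean that inference rests on that one test and the maps merely illustrate it. This stands in part: nothing prescribes a test in each bin. But the same paragraph calls the analyses confirmatory and uses them to show robustness, which a purely descriptive reading does not accommodate.

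A reader might infer several stronger things that the documents do not support:

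- *That the Aim 7 primary test is inflated.* It is a single pre-specified interaction, and the searches do not alter its error.
- *That theta specificity rests wholly on the maps.* Stimulation frequency is a factor in the primary ANOVA, and phase two outcomes are differences from matched arrhythmic stimulation. Only regional specificity and the full-spectrum statement depend on the searches.
- *That Aim 8 makes the same claim.* It refers to Aim 7 for the kind of analysis, says the spread will be explored, and does not repeat the sentence.
- *That Aim 2 supplies a multiplicity procedure which Aim 7 dropped.* Its cluster analysis is there to estimate spread, has no stated error rate, and covers time and space but not frequency. In Aim 7 the comparison with Aim 2 is attached to the time course only.
- *That 74% is the expected error.* It needs independent 1 Hz bins, which is implausible for wavelet estimates.

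For scalp and frequency, chance findings would mostly work against the sponsor's hypothesis. That limits the risk of a falsely favourable claim, but it does not make the statements reliable.

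**Conclusion.** The multiplicity claim in Aim 7 is wrong and should not stand. The defect is confined to what may be concluded about robustness, regional specificity and specificity across the spectrum; no primary or secondary endpoint test changes. If bins were tested at 0.05, the frequency scan alone would carry a 24% to 74% chance of at least one false positive, against a nominal 5%. That range rests on 1 Hz steps, 26 non-target bins, a 24/24 split, an assumed real theta effect and neighbour correlations from 0.95 down to 0. Channels and sliding windows would add to it by an amount that cannot be computed, because their numbers are not given.

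**What to change.** 1. Delete the sentence claiming that the Aim 7 sensitivity analyses are confirmatory and avoid multiplicity.
2. Label the Aim 7 time, scalp and frequency analyses exploratory, as Aims 1 and 6 do for theirs, and give the Aim 8 analyses modelled on them the same label.
3. If any significance is claimed from them, define the family and control family-wise error over the channels, times and frequencies searched, for example with a maximum-statistic or cluster-based permutation test. State whether the searches are read only after a significant primary test.
4. Base any claim of frequency or regional specificity on a direct, corrected contrast of the target with another band or site. The extent of a cluster does not show where an effect stops. Nor does non-significance elsewhere, which section 11.1 itself treats as inconclusive.

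The cost is SAP wording, some computing time and fewer nominally significant points on the maps. Design, sample size and participant procedures do not change.

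### Aim 8 puts a phase angle into an ordinary ANOVA without stating the angle range or how angles are subtracted, and the paired-control subtraction can then create or reverse an alignment effect

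*Combined protocol and SAP*

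**What the plan says.** All of this is in section 11.1.

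- **Outcome.** Aim 8 takes the phase angle of the cross-spectral density between the two sites, averages it over the second half of the train, and reports degrees: "Finally, the angle of the resulting vector is taken to be the average phase lag". No range, wrap point, absolute value or circular method is given.
- **Test.** "Using a two-way ANOVA with factors for TMS frequency (theta or alpha) and TMS alignment (in-phase or anti-phase"). The main hypothesis is an alignment effect "where in-phase decreases the phase lag and anti-phase increases the phase lag". The stronger effect expected for theta is to be "revealed as a significant main effect between TMS frequency and TMS alignment".
- **Delivered lags.** "in-phase stimulation is delivered with zero phase lag and anti-phase stimulation is delivered with a phase lag". Section 2.2 puts the anti-phase lag at 180 degrees.
- **Control rule for Phase Two.** "All analyses will be performed on the difference from condition-matched arrhythmic TMS (in-phase minus arrhythmic-in-synchrony and anti-phase minus arrhythmic-independent"). Of the in-synchrony control the plan says that "activity in the two sites may be synchronized but not in a frequency-specific manner"; of the independent control, "There is no synchronization between the two pulse trains".

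Aim 8 does not say which factor is between participants. Aim 6 does, and section 4.1 randomizes each Phase Two participant to one frequency for both stimulation sessions.

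**The concern.** An angle has no natural start or end, but an ANOVA treats it as a number on a line. The two lags that Aim 8 compares lie on the wrap points of the two usual full-circle scales: 180 degrees is where −180..180 breaks, and 0 degrees is where 0..360 breaks. On either scale, one condition is split between the two ends and its arithmetic mean lands on the opposite side of the circle.

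The control subtraction adds a second difficulty. The plan names the control for each condition but not the arithmetic for angles. Because the two alignments have different controls, any difference between those controls enters the alignment contrast.

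Aim 8 is the plan's check on whether the two sites followed the stimulation as delivered. As written, its answer depends on choices left to the analyst.

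**Working it through.** **The plan's own figure.** Section 11.2 gives N=48 for 95% power at effect size 0.532. A two-sided paired t test at 0.05 reproduces it (power 95.05% at 48). That figure concerns the Aim 1 interaction; the plan gives no power figure for Aim 8.

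**Inputs.** From the plan: delivered lags 0 and 180 degrees, 48 participants, p<0.05, frequency between participants. Assumed, because the plan does not give them:
- a 24:24 split;
- between-participant SD of the lag of 20, 40 or 60 degrees (results in that order below);
- control set A: in-synchrony von Mises at 0 with kappa 2, independent uniform;
- control set B: both controls centred on 45 degrees, kappa 2 and 1.

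**Method.** 4000 simulated trials per setting; angles Normal(centre, SD), then wrapped; alignment main effect of the mixed ANOVA (46 df). *Right* means the anti-phase lag tests larger, *wrong* smaller.

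**Step 1: the wrap.** With von Mises lags at kappa 20 (circular SD about 13 degrees) around 180, the signed values split between the two ends: mean about 0, SD about 170 degrees. Taken unsigned, the same lags average about 170, against about 10 for in-phase.

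**Step 2: full-circle scales.** Centres are in-phase/anti-phase.

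| Centres | Subtraction | −180..180 | 0..360 |
|---|---|---|---|
| 0/180 | none | 5/5/4% | 5/6/5% |
| 0/180 | linear, set A | 5/5/5% | 5/5/6% |
| 0/180 | linear, set B | 7/7/8% | 17/18/18%, nearly all wrong |
| 0/90 | linear, set A | 100/99/82% right | 71/68/47% wrong |
| 10/190 | linear, set A | 69/24/12% wrong | 51/17/10% right |

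Circular subtraction with set A also gives 5/6/5% at 0/180. Subtracting an angle with no preferred direction leaves an angle with no preferred direction, whatever the anti-phase lag was. With set B, the circular difference is right in 99/93/73% if kept on −180..180 and wrong in 99/94/71% if kept on 0..360.

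**Step 3: unsigned lag, no subtraction.** At 0/180 it rejects in 100% of runs at all three SDs; at 0/0 in about 5%; at 0/60 in 70–100%.

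**Step 4: unsigned lag with the required subtraction, true lags identical (0/0).**

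| Order | Set A | Set B |
|---|---|---|
| Take size, then subtract | 100/100/99% wrong | 26/22/19% wrong |
| Subtract, then take size | 100/98/82% right | 26/18/11% right |

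All are false positives, and the two orders have opposite signs. The set A result follows from the controls. A uniform control has mean size 90 degrees and the in-synchrony control about 38.3, so with equal true lags L the first order has expected contrast (L − 90) − (L − 38.3) = −51.7 degrees.

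**Step 5: cos(lag), then subtract.** Scored so that positive means a larger anti-phase lag, the expected contrast is [E cos(in-phase) − E cos(anti-phase)] − [E cos(in-synchrony control) − E cos(independent control)]. Under set A the control bracket is I1(2)/I0(2) − 0 = 0.698. A true 0/60 shift with no spread gives (1 − 0.5) − 0.698 = −0.198, the wrong sign. In simulation the subtracted test is wrong in 99–100% of runs at 0/0 and in 44/54/68% at 0/60.

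**Step 6: limit of the direct contrast.** Unsigned lag and cos(lag) also respond to spread. With both centres at 0, SD 20 against 40 gives 99% rejection for either; SD 40 against 60 gives 72% (unsigned) and 75% (cos). Suppose a lag shift is claimed only if the 95% CI for the mean within-participant circular difference also excludes 0 and those differences have a preferred direction (Rayleigh p<0.05). For cos, the two spread-only rates then fall to 5.5% and 4.5%. Detection stays at 100/100/86–87% for true shifts at 0/180, 0/150, 0/120 and 0/90.

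**The case against.** The strongest defence is that the plan means an unsigned lag. Its hypothesis has one condition shrinking the lag and the other enlarging it, with zero as the in-phase target, and zero is a floor only on a 0–180 scale. This is the most natural reading, and Step 3 shows that it detects 0/180 without difficulty. It stands as an answer to the scale problem, although nothing in the plan converts the angle to a size. It does not answer Step 4.

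A second objection is that Step 4 reflects the mismatch of controls and assumed control lags, not the angle scale. That is partly right: its size falls from near-certainty under set A to 11–26% under set B. But the mismatch is prescribed by the plan, whose own description of the two controls makes set A plausible, and the order of operations is unstated. If size or cosine is taken before subtraction, the bias cancels from the frequency-by-alignment interaction when control lags behave alike in both frequency groups. The alignment main effect, which is Aim 8's main hypothesis, has no such protection.

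Two stronger readings are tempting and are not supported:
- **That the plan has no rule for subtracting the control.** It names the control for each condition; only the arithmetic for angles is missing.
- **That Aim 8 as defined can see perfect entrainment only at chance.** An unstated scale cannot force a result. The chance rate needs a full-circle scale and scatter on both sides of 0 or 180. With no scatter and every anti-phase angle recorded as +180, the difference would be seen.

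The missing between-participants label can be recovered from section 4.1 and Aim 6, and the main-effect wording for two factors is plainly a slip.

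**Conclusion.** The point holds for a secondary outcome and should be settled before analysis. A circular quantity enters a linear ANOVA with neither its range nor its subtraction defined. On a full-circle scale without subtraction, entrainment scattered around 0/180 is found in about 5% of runs. At other centres the choice of scale can decide the sign of a significant result. The unsigned reading cures this, but subtracting different controls then allows a significant alignment effect with identical true lags, in a direction set by the order of operations: 82–100% of runs under set A, 11–26% under set B.

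These sizes rest on assumed spreads, control lags and a 24:24 split. That the range and subtraction are undefined, and that the two alignments have different controls, does not. Aims 6 and 7 and the sample size do not use this metric.

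**What to change.** In the SAP, for Aim 8:

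1. Define the outcome as the unsigned circular lag (0–180 degrees) or cos(lag), or name a circular method.
2. Exempt the deciding test from the Phase Two subtraction rule. Make it the direct within-participant in-phase versus anti-phase contrast, in a mixed ANOVA with frequency between and alignment within participants. Report arrhythmic-subtracted values descriptively only. Do not use transform-then-subtract as the test (Step 5).
3. Report each condition's circular mean direction and resultant length, and claim a lag shift only if mean directions differ, for example by the check in Step 6.
4. Replace the main-effect wording for frequency and alignment together with *interaction*.

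Cost: SAP wording and a little more analysis on the same data, with no new participants. The real loss is that the deciding test no longer removes non-specific effects through the arrhythmic control; the descriptive subtracted values cover that only in part. At SD 60 the check in point 3 also lowers detection of a true 0/180 shift from 100% to about 86%.
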